Secondary Objective: To evaluate the efficacy of oral gepotidacin compared to IM ceftriaxone plus oral azithromycin to treat participants with pharyngeal gonorrhea caused by NG					
Secondary	
Participants with culture-confirmed bacterial eradication of NG from the pharyngeal body site (i.e., pharyngeal microbiological success) at the TOC (Day 4 to 8) Visit without the participant receiving other systemic antimicrobials
 
Refer to Table 5 for further details on the endpoint definition, including the missing data strategy for participants who do not return for the TOC Visit
	
Participants with uncomplicated urogenital and pharyngeal gonorrhea caused by culture-confirmed NG
	
Gepotidacin 2x3000 mg versus Ceftriaxone 500 mg plus azithromycin 1 g, regardless of adherence
	
Difference in proportions (microbiological success rate in the gepotidacin treatment group - ceftriaxone plus azithromycin treatment group)
	
Participants who receive systemic antimicrobials before the TOC Visit will be considered microbiological failures (composite strategy)
 
For study treatment discontinuation, the data will be analyzed as collected (treatment policy strategy)

Estimand Category	Estimand				
	Variable/Endpoint	Population	Treatment Condition	Summary Measure	Intercurrent Event Strategy
Secondary Objective: To evaluate the safety and tolerability of oral gepotidacin compared to IM ceftriaxone plus oral azithromycin					
Secondary (Safety)	Treatment-emergent AEs and serious AEs and change from baseline results for clinical laboratory tests and vital sign measurements	Participants with uncomplicated urogenital gonorrhea	Gepotidacin 2x3000 mg versus Ceftriaxone 500 mg plus azithromycin 1 g, regardless of adherence	The proportions for treatment-emergent AEs and serious AEs will be produced for each arm separately . The means for change from baseline results (clinical laboratory results and vital sign measurements) will be produced for each arm separately .	For study treatment discontinuation, the data will be analyzed as collected (treatment policy strategy)

AE=adverse events; NG=*Neisseria gonorrhoeae*; TOC=Test-of-Cure.

The rationale for a treatment policy intercurrent event strategy of study treatment discontinuation is that interest lies in the treatment effect irrespective of whether the full course of treatment was taken or not, this is reflective of how patients may be treated in clinical practice.

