Adverse events analyses including the analysis of AEs, SAEs and other significant AEs will be based on GSK Core Data Standards. All AEs, study drug related AEs, SAEs, and AEs leading to discontinuation of study treatment or withdrawal from study will be provided in separate listings. The listings will capture the hierarchical relationship between SOC, PT, and verbatim term.

In summary tables where AEs are presented by SOC, PT, and maximum grade, SOCs will be sorted in descending order of the total incidence then alphabetically, PTs will be sorted in descending order of the total incidence then alphabetically within the SOC.

In addition, a summary of the number and percentage of participants with common AEs, defined as AEs with $\geq 1\%$ incidence (before rounding) in any treatment group, will be

presented in descending order of total incidence by PT. The incidence of common AEs with relative risk and associated 95% CI (Wald method) will also be summarized in tables and presented graphically by treatment group.

All deaths occurring any time from informed consent through study completions will be listed. Participant-specific details including date of death, cause of death, and whether the death was attributed to a cardiovascular procedure or surgery will be provided.

For completely missing or partial missing AE start date or end date, imputation rules will be applied following Appendix 5. A listing of *Clostridium difficile* laboratory test results will be provided. The details of data displays are presented in Appendix 9.

AE summaries will also be presented for subgroups defined for safety analysis in Section 5.4.2.

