8.2.3. Acetylcholinesterase-Inhibition Adverse Events

Any reported AE listed in the table in Section 12.4.3 with a start time no later than 12 hours after the last dose administered, as evaluated by the investigator as per the DMID grading criteria provided in in protocol Section 12.5 and Appendix 7, will be included in the programmatic identification of AChE-I related AESI. The list of preferred terms for

programming to be considered due to potential AChE-I is provided in Appendix 4 (Section 12.4.3).

Cumulative grade score of Acetylcholinesterase-Inhibition (AChE-I) will be calculated as the sum of the grade of each reported AE. This enables the number of AEs and the severity of each AE to be considered. The grading scale is defined as

Cumulative Grade:	0	1	2	3	4
Cumulative Grade Score:	0	1 to 3	4 to 6	7 to 10	>=11

For instance, if a participant reports two AEs, one of Grade 1 and the other of Grade 3 their cumulative grade score of 4 would result in cumulative grade 2. This will be calculated for All AChE-I events, non-GI AChE-I events and GI AChE-I events.

Acetylcholinesterase inhibition AESIs will be listed and tabulated by SOC and preferred term and maximum grade. Non-GI AChE-I events will also be summarized. A separate table will summarize the AChE-I AESI by the number of events and unique preferred terms. In addition, time of onset (time from first dose to the onset of first event in hours), duration, and lag time (the time from last dose to the end date/time of the last event for subjects whose end date/time of the last event is after treatment end date/time) of AChE-I event will also be summarized and repeated for non-GI AChE-I and GI AChE-I events. AChE-I events with a start time less than 6 hours after the latest dose administered will also be flagged in listings.

Graphical presentation via stacked bar charts of percentage of subjects in each AChE-I cumulative grade will be produced for All AChE-I events and non-GI AChE-I events separately. In addition, a forest plot of relative risk of AChE-I events between two treatment groups and its 95% Wald CI for each event will also be included. The details of the planned displays are provided in Appendix 9.

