8.5.2. Quantitative Screening for Identification of Potential ARs

Frequentist approach to screen for potential ARs will be used. Specifically, the Crowe method [Crowe B, et al, 2013] will be applied for initial screening of the large number of adverse events to generate a “short list” of potential ARs. This method is based on three measures:

- Absolute incidence rate (%) in control arm (ceftriaxone plus azithromycin),
- Estimate of treatment effect (Relative Risk [RR]) relative to active control arm (ceftriaxone plus azithromycin),
- An estimate of variability around the treatment effect (95% CI for RR).

High Level Terms (HLTs) will be used to group adverse events and the screening for potential ARs will be conducted at HLT level. Quantitative screening criteria for potential ARs endorsed by the Safety Review Team (SRT) are displayed in the following table:

Criterion	Absolute Incidence in ceftriaxone plus oral azithromycin	HLT RR (Gepotidacin vs ceftriaxone plus azithromycin)	95% CI for HLT RR*
1	No conditions	No conditions	Lower CI > 1
2	≥5%	≥1.25	No conditions
3	<5%	≥1.50	No conditions

*95% CI for RRs determined using Wald method.

For each criterion, it is necessary to have all the features described in the column headings in order for the event to be considered to have achieved that particular criterion. Events may meet more than one criterion. Events that meet at least one of the criteria are shortlisted as a potential AR.

Based on 310 participants being exposed to Gepotidacin, there is a 90% chance of observing at least one particular adverse event if the true incidence rate of that adverse event is not below 0.75%. When the active control arm has zero events, the estimate of relative risk (RR) would be undefined and therefore cannot be evaluated using the quantitative screening criteria given above. The screening criteria in this case will be based on the minimum number of subjects with the event of interest in gepotidacin arm (vs 0 in ceftriaxone plus azithromycin arm). At least 3 participants with the AE of interest must be observed in the gepotidacin arm in order to be included in the “short list” of potential ARs.

A summary table of treatment emergent adverse events by SOC, HLTs and PTs with incidence (%) for each treatment group, RR and the associated 95% CI will be generated. An additional table will be produced displaying only the adverse events meeting the pre-specified quantitative screening criteria.

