10. BENEFIT/RISK

Forest plots showing the treatment effect and confidence intervals related to benefits and risks of treatment with gepotidacin will be created. Benefits will be represented by risk differences and corresponding confidence intervals from the following analyses based on the Micro-ITT analysis population:

- Microbiological outcome and response rate of urogenital Gonorrhea at the TOC Visit (primary analysis),
- NAAT outcome and response rate of urogenital Gonorrhea at the TOC Visit (exploratory analysis).

For these analyses, risk differences and 95% confidence intervals will be determined using the methods described in Section 7.1.6.1 and Section 7.3.1.5, respectively. Additionally, relative risks and corresponding 95% confidence intervals will be displayed for the following safety endpoints: incidence of AEs, SAEs and, separately, CV, GI, *C. difficile*, and AChE-I AESIs using the Safety analysis population. Confidence intervals for relative risks will be determined using the asymptotic Wald method.

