12.9.9. Safety Figures

Safety: Figures					
No.	Population	IDSL / Example Shell	Title	Programming Notes	Deliverable
3.101.	Safety	AE10	Plot of Common ($\geq 1\%$) Adverse Events and Proportion of Participants		DS, SAC
3.102.	Safety	AE11	Cumulative Distribution of Time to First Gastrointestinal Event		DS, SAC
3.103.	Safety	EFF_F3	Stacked Bar Chart of Acetylcholinesterase Inhibition Cumulative Grade	
Programming note: Y axis label is "Percentage of Subjects (%)" colors should not use red or blue to avoid misinterpretation with treatment arms. Grade scale is 0 best-case for participant to 4 worst case for participant.
 
Ordering of AChE-I grouping.
 
 AChE-I non-GI AChE-I 	DS, SAC
3.104.	Safety	EFF_F3	Stacked Bar Chart of non- Gastrointestinal Acetylcholinesterase Inhibition Cumulative Grade		DS, SAC
3.105.	Safety	EFF_F3	Bar Chart of Gastrointestinal Events by Grade in Percentage of Participants over Time		DS, SAC
3.106.	Safety	AE10	Plot of Acetylcholinesterase Inhibition Events Relative Risk		DS, SAC
3.201.	Safety	LIVER14	Plot of Maximum Post-Baseline vs Baseline Alanine Aminotransferase		DS, SAC
3.202.	Safety	LIVER9	Plot of Maximum Total Bilirubin vs Maximum Post Baseline Alanine Aminotransferase		DS, SAC

Safety: Figures					
No.	Population	IDSL / Example Shell	Title	Programming Notes	Deliverable
3.203.	Safety	LB11	Liver Function Tests Participant Profiles		DS, SAC
BENEFIT/RISK					
3.301.	Micro-ITT, Safety	EFF_T4	Forest plot for Benefit/Risk		DS, SAC
Adverse Events (Adverse Reactions)					
3.401	Safety	Template Visual 1 double dot plot	Dot Plot for Treatment Emergent Adverse Events by High Level Term - Safety		DS, SAC
3.402.	Safety	Template Visual 3 Heatmap	Heatmap of Risk Ratios for Treatment Emergent Adverse Event High Level Terms that Meet the Screening Criteria by System Organ Class - Safety		DS, SAC
3.403.	Safety	Template Visual 5 Kaplan Meier curve	Kaplan Meier Curve for Treatment Emergent Potential AR Event by Treatment - Safety		DS, SAC

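### Harm contrasts in SAP 8.1, 8.2.3 and 10 are planned only as Wald relative risks, which give no interval for a rare event absent from one arm; a score risk difference should sit beside them

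*SAP*

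**What the plan says.** SAP 8.1: "The incidence of common AEs with relative risk and associated 95% CI (Wald method) will also be summarized in tables". The display is also graphical, and a common AE is one with at least 1% incidence in any treatment group.

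SAP 8.2.3 plans "a forest plot of relative risk of AChE-I events between two treatment groups and its 95% Wald CI for each event".

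SAP 10 (benefit/risk): "Benefits will be represented by risk differences and corresponding confidence intervals". For harms, "relative risks and corresponding 95% confidence intervals will be displayed for the following safety endpoints": AEs, SAEs and, separately, CV, GI, *C. difficile* and AChE-I AESIs. On the interval method it says: "Confidence intervals for relative risks will be determined using the asymptotic Wald method". The display list in SAP 12.9.9 has one entry, Figure 3.301, titled "Forest plot for Benefit/Risk".

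SAP 8.5.2 (adverse-reaction screening): "When the active control arm has zero events, the estimate of relative risk (RR) would be undefined and therefore cannot be evaluated". For that case it substitutes a count rule: at least 3 gepotidacin participants with the event against none on the comparator puts the event on the short list. SAP 8.5 says these outputs are reported separately from the CSR.

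Protocol Section 4, Table 3, gives the safety estimand's summary measure: "The proportions for treatment-emergent AEs and serious AEs will be produced for each arm separately".

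SAP Section 7 has a zero-cell constant (1E-10), but only for efficacy risk differences when both arms show 0% or both show 100% success.

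**The concern.** The SAP text describes no between-arm risk difference for any harm. The one contrast it plans has no value, or no interval, when an arm has zero events. The SAP recognises this in 8.5.2, but solves it only for a screening list.

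Three displays are left without a rule. In the common-AE table, an event can qualify on the gepotidacin arm alone and have no ratio. In the AChE-I plot, individual terms may be absent from one arm. In the benefit/risk figure, SAEs and *C. difficile* are named rows, and SAP 8.5.2 expects the incidence of serious and severe AEs to be very low. At programming such a row would be left blank or filled by an improvised correction.

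A second consequence follows in Section 10: benefits are given in percentage points and harms only as ratios, so the figure does not let a reader see harms on the absolute scale used for benefits.

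**Working it through.** **Inputs.** Gepotidacin exposure of 310 is stated in SAP 8.5.2. For the comparator, 310 is an assumption: about 620 randomized 1:1 (SAP 2.3) gives 620/2 = 310. The Wald interval is taken to be on the log scale.

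**The plan's own figure.** SAP 8.5.2 states a 90% chance of seeing at least one event at a true incidence of 0.75% with 310 exposed. 1 − (1 − 0.0075)^310 = 0.903, so it reproduces.

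**Why the planned contrast fails.** With x1 and x2 events among n1 and n2 participants:

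- RR = (x1/n1)/(x2/n2)
- SE(log RR) = √(1/x1 − 1/n1 + 1/x2 − 1/n2)

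If x2 = 0 the RR divides by zero. If x1 = 0 the RR is 0, but its log and the 1/x1 term are not finite. So x v 0 has neither RR nor limits, and 0 v x has an RR of 0 without limits.

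**How often.** P(no comparator events) = (1 − p)^310:

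| True comparator rate | P(no events) |
|---|---|
| 0.1% | 73% |
| 0.2% | 54% |
| 0.3% | 39% |
| 0.5% | 21% |
| 1% | 4.4% |
| 2% | 0.2% |

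If both arms share the rate, the chance that at least one arm is empty is 1 − (1 − P)²: 93%, 79%, 63% and 38% for the first four rows.

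**What enters the common-AE table.** 1% of 310 is 3.1, so 4 participants qualify an event. A 4 v 0 event is therefore tabulated with no RR.

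**What a score interval gives.** The Miettinen-Nurminen 95% limits are the values d at which (x1/n1 − x2/n2 − d)/√V(d) = ±1.96. Here V(d) = [p1(1 − p1)/n1 + p2(1 − p2)/n2] × N/(N − 1), with N = n1 + n2 and p1 = p2 + d fitted under the constraint.

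| Gepotidacin v comparator | Planned RR (Wald CI) | Risk difference, points (MN 95% CI) | Fisher two-sided p |
|---|---|---|---|
| 3 v 0 | undefined | +0.97 (−0.26 to 2.81) | 0.25 |
| 4 v 0 | undefined | +1.29 (0.06 to 3.27) | 0.12 |
| 6 v 0 | undefined | +1.94 (0.70 to 4.16) | 0.03 |
| 10 v 0 | undefined | +3.23 (1.76 to 5.84) | 0.002 |
| 0 v 0 | undefined | 0 (−1.2 to +1.2) | – |

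Hand check of the 6 v 0 lower limit: at d = 0.0070 the constrained fit is p1 = 0.0097 and p2 = 0.0027. √V = √[(0.00962 + 0.00270)/310 × 620/619] = 0.0063, and (0.01935 − 0.0070)/0.0063 = 1.96.

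**Would adding 0.5 rescue the ratio?** For 6 v 0 it gives RR 13.0 (0.74 to 229.8), an interval too wide to be useful.

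**The case against.** The best defence is that little is hidden. The safety estimand asks only for per-arm proportions, and these are reported whatever happens to the ratio. In SAP 8.5.2, AESIs and serious or severe AEs go on the adverse-reaction short list automatically, as does any high-level term at 3 or more against 0. SAP 8.5.3 then gives each listed event subgroup, grade and time-to-occurrence displays. All of this stands, and it limits the point to a missing estimate and interval.

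Four stronger readings are tempting but not supported:

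- *The most important imbalances drop out.* Only events with zero in one arm lose the contrast. Protocol 3.3.1 lists GI effects for both comparator drugs, so the main expected harms should occur in both arms. Even at a 1% comparator rate the chance of an empty arm is about 4%.
- *4 v 0 is a clear signal.* The score interval just excludes zero, but Fisher's p is 0.12. With many terms and no multiplicity adjustment it is borderline.
- *Ratios and differences will share one axis.* Section 10 speaks of forest plots in the plural. Figure 3.301 cites a shell (EFF_T4) also used for MIC distribution tables, so the layout cannot be confirmed and separate panels are possible.
- *GI and AChE-I rows double count harm.* The rows overlap in terms such as nausea, vomiting and diarrhoea, but they are displayed separately and nothing is summed. AChE-I also has a 12-hour onset limit. Replacing it with non-GI AChE-I would drop a predefined AESI.

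**Conclusion.** The point holds as a limited gap in descriptive safety reporting. In SAP 8.1, 8.2.3 and 10 the only specified harm contrast cannot be computed for rare events absent from one arm, and the 8.5.2 rule flags such events without estimating anything. The gap is material at true comparator rates up to about 0.5% (21% to 73% chance of no comparator events) and negligible from about 2%. The clearest loss is an imbalance such as 6 v 0, where a usable interval exists but is not planned.

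These figures assume 310 treated per arm. The documents give no expected rates for SAEs or *C. difficile*, so which rows would be empty cannot be predicted. The primary efficacy conclusion and data collection are unaffected. The change is worth making because it is cheap and its method is already in the SAP.

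**What to change.** In SAP 8.1, 8.2.3 and 10 (Tables 3.106 and 3.107; Figures 3.101, 3.106 and 3.301):

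1. Add the risk difference, gepotidacin minus comparator, with an unstratified Miettinen-Nurminen 95% CI. No zero-cell device is needed for x v 0. The Section 7 constant is needed only for 0 v 0, and its scope would have to be extended to these safety displays.
2. Keep the relative risk with Wald CI where both arms have events, and state that it is not shown otherwise.
3. In the benefit/risk figure, show the harms' risk differences so that they can be read on the absolute scale used for benefits. Keep the all-AChE-I row; a non-GI AChE-I row may be added to make the overlap with GI AESIs visible.
4. Label the intervals as descriptive and unadjusted for multiplicity.

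The cost is SAP wording, reuse of the efficacy method, and one extra column or panel per display. The downside is that borderline unadjusted intervals may be over-read, which the labelling is meant to limit.

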12. APPENDICES

12.1. Appendix 1: Schedule of Activities

12.1.1. Protocol Defined Schedule of Events

Table 5 Schedule of Activities

Procedure	Visit ^a	Baseline		TOC ^b	Follow-up ^c	Early Withdrawal
	Study Day	1		4 to 8	14 to 21	NA
		Predose	Postdose	NA	NA	NA
Written informed consent/assent		X				
IRT – Screening module		X				
Inclusion and exclusion criteria		X				
Participant demography		X				
Participant social and sexual history ^d		X				
Medical/surgical history		X				
Diagnosis of presumptive uncomplicated urogenital gonorrhea		X				
Bacteriology samples ^e		X		X	X	X
NAAT assay samples ^f		X		X	X	X
Physical examination (including height and weight at Baseline only) ^g		X		X		
12-lead electrocardiogram ^h		X				
Vital sign measurements ⁱ		X		X		
Hematology, chemistry, and urinalysis		X		X		
Serology (hepatitis B and C and HIV) ^j		X				
Urine pregnancy test ^k		X ^k		X		X
Drug and alcohol screen		X				
IRT – Randomization module		X				
Administer oral gepotidacin ^l			X ^l			
Administer IM ceftriaxone plus oral azithromycin ^m			X ^m			
Sexual history since last visit ^d				X	X	X
Serious adverse events ⁿ		X	X	X	X	X
Adverse events ^o			X	X	X	X
Concomitant medication review		X	X	X	X	X
Schedule TOC and Follow-up Visits		X ^{p,q}		X ^q	X ^p	
Treatment for CT and/or Mgen infection ^r				X	X	X
Genetic sample ^s		X				

CT=*Chlamydia trachomatis*; HIV=human immunodeficiency virus; IM=intramuscular; Mgen=*Mycoplasma genitalium*; NA=not applicable; NAAT=nucleic acid amplification test; TOC=Test-of-Cure.

- a. For all study visits, to minimize the amount of time that participants spend at the clinic, eConsent may be utilized and remote collection of study-related data may be obtained as described in the Study Reference Manual. Thus, some visit data may be collected through a combination of telemedicine and on-site visits. Collection of information via telemedicine will be performed only where local regulations permit.
- b. TOC (Day 4 to 8) Visit: Participants will be instructed to return to the study site within 3 to 7 days after study treatment administration. This visit may occur earlier if participants experience an adverse event.
- c. Participants will be instructed to return to the study site from Day 14 to 21 for a Follow-up Visit. The investigator and/or study site staff should make every effort to ensure the participant returns for this visit. If the participant is unable to return to the study site, the visit assessments may be completed via telephone, with the exception of assessments requiring sample collection for laboratory testing.
- d. Refer to the Study Reference Manual for information to collect for social and sexual history.
- e. See Table 6 for collection of bacteriology samples. Also refer to the laboratory manual.
- f. See Table 6 for collection of NAAT assay samples. Also refer to the laboratory manual.
- g. A complete physical examination will be performed at the Baseline Visit and a gonorrhea-focused examination will be performed at the TOC Visit (see Protocol Section 9.4.1). Height and weight will only be measured and recorded at the Baseline Visit (before dosing).
- h. See Protocol Section 6.2 for electrocardiogram exclusion criterion for participants aged ≥ 12 to < 18 years. For additional details see Protocol Section 8.1.2 and Section 9.4.3.
- i. Take measurement of temperature, blood pressure, and pulse rate. See Protocol Section 9.4.2.
- j. If serology testing was performed within 3 months prior to the first dose of study treatment and results were positive, testing at Baseline is not required. If testing was performed within 3 months and any result was negative, testing at Baseline is required.
- k. For women of childbearing potential, a negative urine pregnancy test is sufficient for eligibility. See Protocol appendix 6 for Baseline urine test sensitivity requirements and associated contraception requirements.
- l. During the Baseline Visit, participants randomly assigned to gepotidacin will receive their first oral dose (3000 mg) at the study site. Participants will self-administer their second dose (3000 mg) as an outpatient 10 to 12 hours after the first dose; however, for participants who weigh < 50 kg or have moderate renal impairment, the second dose should be taken approximately 12 hours after the first dose). See Protocol Section 7.1. Each dose should be taken after food consumption and with water to assist with tolerability. Participants will be contacted to confirm that they took their second gepotidacin dose. See Protocol Section 7.6.
- m. During the Baseline Visit, participants randomly assigned to ceftriaxone plus azithromycin will receive a single IM dose of ceftriaxone (500 mg) plus a single oral dose of azithromycin (1 g). See Protocol Section 7.1. Azithromycin should be taken after food consumption and with water.
- n. Record serious adverse events from the time of consent/assent in order to fulfill international regulatory requirements.
- o. Record adverse events from the time of the first dose of study treatment.
- p. Confirm return day/time for the TOC and Follow-up Visits.
- q. Previsit reminder: Study site staff will contact the participant 24 ± 4 hours before the respectively scheduled Baseline (if applicable), TOC, or Follow-up Visit.
- r. Participants who tested positive for CT and/or Mgen per NAAT results at the Baseline Visit should be treated per local standard of care at or after the TOC Visit or at the Follow-up Visit (if treatment has not already been initiated), as required, after all study procedures at the visit have been completed.
- s. Collect sample only if the participant has a signed consent/assent specific for this purpose. The Baseline Visit is the recommended time to collect the sample; however, it can be collected at any time during the study.

Table 6 Collection of Bacteriological Microbiological Specimens

	Visit Study Day	Baseline 1	TOC ^a 4 to 8	Follow-up 14 to 21	Early Withdrawal NA
Collection Type					
Anatomical Site^b – Organism		Pre-dose	NA	NA	NA
Bacteriology sample collection^b					
Urogenital – NG ^c		X	X		X
Pharyngeal – NG ^d		X	X	X ^e	X
Rectal – NG ^d		X	X		X
NAAT assay sample collection^f					
Urogenital – NG and CT ^g		X	X ^h		X
Urogenital – Mgen ^g		X		X ⁱ	X
Pharyngeal – NG and CT ^j		X	X	X ^k	X
Rectal – NG and CT ^j		X	X		X

NA=not applicable; NG=*Neisseria gonorrhoeae*; TOC=Test-of-Cure.

CT=*Chlamydia trachomatis*; Mgen=*Mycoplasma genitalium*; NA=not applicable; NAAT=nucleic acid amplification test; NG=*Neisseria gonorrhoeae*; TOC=Test-of-Cure.

- a. Any participant that withdraws before TOC should have all bacteriology and NAAT assay collections performed as indicated at the TOC Visit.
- b. Multiple swab specimens and types may need to be obtained from each anatomical site; refer to the laboratory manual.
- c. Collect a pretreatment urogenital swab specimen from all participants for Gram stain (males and females), bacterial culture, and in vitro susceptibility testing at Baseline. At TOC, a urogenital swab specimen will be collected for Gram stain, bacterial culture, and in vitro susceptibility testing. Note: All urogenital swab specimens will be processed for Gram stain testing following inoculation of the culture plates.
- d. Pretreatment rectal and pharyngeal swab specimens for bacterial culture and in vitro susceptibility testing will be obtained from participants who are willing to provide such specimens, regardless of known exposure. At TOC, swab specimens will be collected from pharyngeal and/or rectal sites that were collected at Baseline for bacterial culture and in vitro susceptibility testing. Note: None of the rectal or pharyngeal swab specimens will be processed for Gram stain testing.
- e. At Follow-up, pharyngeal swab specimens will be obtained for bacterial culture and in vitro susceptibility testing from participants who had a positive NAAT assay for pharyngeal NG at both Baseline and TOC. Results from the NAAT assay will be available to the study sites by the Follow-up Visit.
- f. See the laboratory manual for local versus central laboratory details and the number and type of specimens to collect.
- g. Pretreatment baseline urogenital specimens will be obtained from all participants for detection of NG, Mgen, and CT by NAAT. At Baseline, while detection of NG and CT by NAAT may be performed using the same urogenital sample, 2 separate samples must be obtained (1 for the local laboratory and 1 for the central laboratory).
- h. Urogenital specimens will be obtained from all participants for detection of NG and CT by NAAT at the TOC Visit.
- i. At Follow-up, a urogenital specimen will be collected for the detection of Mgen only by NAAT from participants who had a positive NAAT assay for Mgen at Baseline. Results from the NAAT assay will be available to the study sites by the Follow-up Visit.
- j. Pretreatment baseline pharyngeal and rectal specimens for detection of NG and CT by NAAT will be obtained from participants who are willing to provide such specimens, regardless of known exposure. At TOC, a specimen will be collected from pharyngeal and/or rectal sites that were collected at Baseline.
- k. At Follow-up, a pharyngeal specimen will be collected for detection of NG and CT by NAAT from participants whose NAAT assay had the presence of nucleic acid for NG at both Baseline and TOC. NAAT assay results will be available to the study sites by the Follow-up Visit.

Table 7 BTZ116577 NAAT Overview by Body Site and Organism

Body site	Organism	Baseline Visit			TOC Visit		F/U Visit	
		Local Lab	Central Lab		Central Lab		Central Lab	
			Real Time	Batch	Real Time	Batch	Real Time	Batch
Urogenital	NG/CT	X	X		X			
	MGen			X				X ^b
Pharyngeal ^a	NG/CT		X		X		X ^c	
Rectal ^a	NG/CT		X		X			

NG = *N. gonorrhoeae*; CT = *C. trachomatis*; MGen = *M. genitalium*; RT = real time (processed upon arrival); F/U=Follow-up.

a. Optional (upon patient consent)

b. Only if positive NAAT at baseline visit. MG NAATs will be run weekly by the central lab, so that baseline and results are back to the site in time for F/U.

c. Only if positive NG NAAT at baseline and TOC visit. Sites will have baseline and TOC pharyngeal NAAT results back by F/U

Note: Only central laboratory NAAT results will be used in the exploratory analysis, local lab NAAT is conducted to guide therapy at the TOC visit (*Chlamydia trachomatis*)

